6.1 Efficacy Assessments

Response to treatment in this study will be evaluated using the international criteria proposed by the RECIST Committee (Therasse et al. 2000a), modified in 2009 (Eisenhauer et al. 2009) and clarified for disease-specific adaptation (Schwartz et al. 2016). The primary efficacy endpoint, BORR, will be evaluated using RECIST v1.1 (**Section 6.1.1.1**).

6.1.1 Response Evaluation Criteria in Solid Tumors (RECIST) v1.1

Tumor response will be evaluated according to RECIST guidelines (Therasse et al. 2000b) using tumor imaging (see **Section 6.1.1.1** for tumor imaging details).

Assessment by RECIST v1.1 will be done at 12-week intervals as specified in **Table 3-1**. Lesions will be numbered identically for each visit as target and non-target, new lesions (see definitions in **Table 6-1**). Tumor assessments during the Core study (over 24 weeks) will be

done by independent central radiologic review¹ and integrated medical oncologist disease assessment based on RECIST v1.1 and investigator assessment of RECIST and iRECIST (will be throughout the study).

In support of RECIST v1.1, when more than one accessible and measurable tumor is present at baseline, all lesions (those with the longest diameter(s)/ organ that are measurable in the physicians' discretion) up to 2 cutaneous lesions should be identified as measurable representative Target Lesions. A target lesion may be a treated or untreated lesion.

An 'accessible lesion' is defined as a cutaneous or subcutaneous lesion that can be reached from the surface with the electroporation needle array (with depth of up to 1.5 cm from the surface). Refer to section 5.1.1.3.

Each patient will be assigned a response category (**Table 6-1**)

Table 6-1 Response Evaluation Criteria in Solid Tumors v1.1): complete response (CR), partial response (PR), stable disease (SD), progressive disease (PD).

Per RECIST 1.1, partial response (PR) or complete response (CR) should be confirmed by a repeat tumor imaging assessment not less than 4 weeks from the date the response was first documented. The tumor imaging for confirmation of response may be performed at the earliest 4 weeks after the first indication of response, or at the next scheduled scan (i.e. 12 weeks later), whichever is clinically indicated.

¹ In accordance to FDA "Clinical Trial Imaging Endpoint Process Standards Guidance for Industry" (Version 1 March 2015);

<http://www.fda.gov/downloads/drugs/guidancecomplianceregulatoryinformation/guidances/ucm268555.pdf>

Table 6-1 Response Evaluation Criteria in Solid Tumors v1.1

RECIST v1.1 Response Criteria	Target Lesions	Non-Target Lesions
Complete Response (CR)²	Disappearance of all target lesions, determined by two separate observations conducted not less than 4 weeks apart. Any pathological lymph nodes (whether target or non-target) must have reduction in short axis to <10 mm (the sum may not be "0" if there are target nodes). There can be no appearance of new lesions.	Disappearance of all non-target lesions and normalization of tumor marker level. All lymph nodes must be non-pathological in size (<10 mm short axis).
Partial Response	At least a 30% decrease in the sum of the longest diameter (LD) of target lesions, taking as reference the baseline sum LD. There can be no appearance of new lesions.	Non-target lesions must be non-PD.
Stable Disease (SD)	Neither sufficient shrinkage to qualify for PR nor sufficient increase to qualify for PD, taking as reference the smallest sum LD since the treatment started.	Persistence of one or more non-target lesion(s) and/or maintenance of tumor marker level above the normal limits.

² Patients will meet the primary endpoint (BORR) if they attain a confirmed CR or PR over the 24 weeks with the combination treatment with a 4-week confirmatory scan per RECIST v1.1.

Progressive Disease (PD)	At least a 20% increase in the sum of diameters of measured lesions taking as references the smallest sum of diameters recorded on study (including baseline) AND an absolute increase of ≥ 5 mm, or the appearance of one or more new lesions.	Appearance of one or more new lesions and/or unequivocal progression of existing non-target lesions.
---------------------------------	--	--

6.1.1.1 Evaluation of Best Overall Response with RECIST v1.1

The best overall response (BOR) is the best response recorded from the start of the treatment until disease progression/recurrence (taking as reference for progressive disease the smallest measurements recorded since the treatment started). The patient's best response assignment will depend on the achievement of both measurement and confirmation criteria (**Table 6-2**).

Table 6-2: Overall Response Definitions using RECIST v1.1

Target Lesions	Non-Target Lesions	New Lesions	Overall Response	Best Response for this Category Also Requires
CR	CR	No	CR	Normalization of tumor markers, tumor nodes <10 mm
CR	Non-CR/ Non-PD	No	PR	
CR	Not all evaluated	No	PR	
PR	Non-PD / No all evaluated	No	PR	
SD	Non-PD	No	SD	Documented at least once ≥ 4 weeks from baseline
Not all evaluated	Non-PD	No	NE	
PD	Any	Any	PD	

Any	PD*	Any	PD	
Any	Any	Yes	PD	

* In exceptional circumstances, unequivocal progression in non-target lesions may be accepted as disease progression Source: (Seymour et al. 2017)

Other definitions

- Progression free survival (PFS) – PFS is defined as the time, in months, from the first dosing date until the date of disease progression (i.e., the date of the tumor imaging) or death from any cause. RECIST v1.1 will be used to determine the dates of progression as this methodology is accepted by regulatory authorities. In addition, final determination of radiologic progression will be based on the central imaging vendor assessment of progression, rather than site study team assessment. Determination of radiologic progression as determined by central imaging vendor (verification of PD) will be communicated to the site study team.

7 Statistical Plan

7.1 Sample Size Justification

Dose Expansion Phase, Stage 1: We expect to enroll 30 patients in both arms (15 patients in Arm A and 15 patients in Arm B). We will allow patients who were enrolled in the dose escalation safety lead-in to enroll in Arm A of Stage 1, depending on the final dose.

Dose Expansion Phase, Stage 2: Depending on the results of the clinical data in Stage 1, Stage 2 will enroll up to an additional 26 patients accordingly:

If there are at least ≥ 3 responses in 15 patients, in either Arms A or B, up to an additional 26 patients (13 patients in Arm A and 13 patients in Arm B) will be enrolled in the respective treatment arms.

The above Simon 2-stage sample sizes were based on the following assumptions: the objective response rate for pembrolizumab is approximately 15%³ and we suggest that a 20% absolute improvement in this response rate would be clinically meaningful. We propose to test the hypothesis that the objective response rate for the combination of tavo-EP with pembrolizumab and epacadostat is 35% versus the null hypothesis that it is similar to the response rate for pembrolizumab monotherapy, 15%. The statistical power calculations are based on the Simon Two-Stage Optimal Design¹¹ with a Type I error rate of 0.05 and power of 80%.

Efficacy Assessment:

The objective response rate for pembrolizumab is approximately 15%³ and we suggest that a 20% absolute improvement in this response rate would be clinically meaningful. We propose to test the hypothesis that the objective response rate for the combination of tavo-EP with pembrolizumab and epacadostat is 35% versus the null hypothesis that it is similar

to the response rate for pembrolizumab monotherapy, 15%. The following statistical power calculations are based on the Simon Two-Stage Optimal Design¹¹ with a Type I error rate of 0.05 and power of 80%.

7.2 Analysis Populations

The analysis population is defined as All Treated Subjects, defined as all enrolled subjects who received at least one dose of study treatment. Efficacy and safety analyses will be completed in the All Treated Subjects population.

7.3 Primary Efficacy Analysis

The primary efficacy analysis will be conducted on All Treated Subjects, by treatment arm and dose levels as appropriate, and overall. The primary endpoint of BORR will be calculated and applied in the proceeding of Simon two-stage design, however, no formal statistical testing will be conducted between dose levels or between treatment arms as the sample size is not powered adequately for the testing, and comparisons will be made in a qualitative fashion.

Patients' best overall response will be summarized by the number and percentage of subjects who achieved a CR, PR, SD and PD. BORR is calculated as the percentage of patients who achieved a CR or PR relative to the total size of the All Treated Subjects population. The 95% confidence interval of BORR will be calculated by the Clopper-Pearson (exact binomial) method.

The primary endpoint of safety will be performed for all patients having received at least one dose of study drug. The study will use the NCI CTCAE v4.0.

7.4 Secondary/ Exploratory Efficacy Analysis

All secondary and exploratory efficacy analyses will be conducted on All Treated Subjects, by treatment arm and dose levels as appropriate, and overall.

The secondary endpoints of PFS and OS will be analyzed and plotted using the Kaplan-Meier method, estimates of the median will be provided and the 95% CI of median will be calculated by the Brookmeyer and Crowley method.

Time to response is defined as the number of days from the date of enrollment to the date of the first documented response of CR or PR. Time to response will be summarized by descriptive statistics including mean, median, and standard deviation, minimum and maximum.

Disease control rate (DCR) is defined as the percentage of patients who achieved a best overall response of CR, PR or SD. Clinical benefit rate (CBR) is defined as the percentage of patients who achieved a best overall response of CR, PR and SD with a duration of at least 6 months or longer. DCR and CBR will be analyzed using the method similar to BORR.

Duration of response (DOR) will be calculated for patients who achieved a best overall response of CR or PR, and calculated as the number of days from the date when CR or PR is first met to the date of progression or death. Patients who do not have a documented progression or death will be censored on the last date of tumor assessment. The number and percentage of patients whose DOR is longer than certain milestone times (such as 6 months,

9 months and 12 months) will be quantified. If the number of responders is sufficient, DOR may also be analyzed using the Kaplan-Meier method, with the median DOR and 95% CI calculated similar to PFS and OS analysis.

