--	---

Duration of Therapy	
Dose Escalation Safety Lead-In Phase: 6 patients will receive triplet therapy for 30 days at Dose level 0. After 30 days of therapy, if those patients do not experience a DLT, an additional 6 patients will be enrolled at the next Dose level, Level 1 which will increase epacadostat to 600 mg for 30 days, tavo-EP and pembrolizumab will not be dose escalated. If no patients experience a DLT at 600 mg, that will be the dose level of epacadostat used in Stage 1, for both Arms A and B.
 
Dose Expansion Phase, Stage 1, Arm A: Patients will receive triplet therapy for 12 months or until the development of an unacceptable treatment associated toxicity or confirmed progression. After 12 months of therapy, patients will enter the follow-up phase for the next 24 months. Patients with disease progression during the follow-up phase will have access to 12 additional months of triplet therapy. Patients who are eligible for treatment on study but who have experienced regression of all previously accessible lesions may continue on pembrolizumab and epacadostat without tavo-EP.
 
Dose Expansion Phase, Stage 1, Arm B: Patients will receive combination therapy for 12 months or until the development of an unacceptable treatment associated toxicity or confirmed progression. After 12 months of therapy, patients will enter the follow-up phase for the next 24 months.
 
Dose Expansion Phase, Stage 2: Depending on the results of the clinical data in Stage 1, Stage 2 will enroll up to an additional 26 patients accordingly:
 
If there are at least ≥ 3 responses in 15 patients, in either Arms A or B, up to an additional 26 patients (13 patients in Arm A and 13 patients in Arm B) will be enrolled in the respective treatment arms.

Duration of Follow up	Patients will be followed at 3 month intervals for toxicity and radiographic imaging 1) until start of a new anti-cancer treatment, (2) until 30 days after documented disease progression, (3) until death, or (4) until 36 months from the initiation of treatment on study, whichever comes first. Each subject will be followed for overall survival until death, withdrawal of consent, or the end of the study, whichever occurs first.
Duration Of Study	Study accrual will be sufficient to assess the primary endpoint within 24 months from the time the study opens to accrual.

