2.2 Secondary

Dose Expansion:

- Determine the durability of clinical benefits in patients treated with tavo-EP, pembrolizumab, and epacadostat as assessed by time to progression, median PFS, median OS

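### Duration-of-response milestones are planned as raw percentages of a censored variable, with no rule for responders censored before the milestone

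*Combined protocol and SAP*

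**What the plan says.** Section 7.4 defines DOR for patients with a best response of CR or PR, "calculated as the number of days from the date when CR or PR is first met to the date of progression or death". It adds: "Patients who do not have a documented progression or death will be censored on the last date of tumor assessment". The summary it commits to is "The number and percentage of patients whose DOR is longer than certain milestone times", with 6, 9 and 12 months as examples. It does not name the denominator, a minimum follow-up, or how to class a responder censored before a milestone.

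Kaplan-Meier follows as an option: "If the number of responders is sufficient, DOR may also be analyzed using the Kaplan-Meier method". Sufficient is not defined, and the only outputs named are the median and its 95% confidence interval. In the same section PFS and OS go to Kaplan-Meier without condition. The Statistical consideration row of the synopsis assigns Kaplan-Meier to time-to-event variables in general, also without condition.

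No data cut-off is given for DOR. Section 4.5 ends imaging at new anti-cancer treatment, 30 days after progression, death, or 36 months from the start of treatment, whichever is first.

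**The concern.** A raw percentage above a milestone is sound only if every responder has been followed to that milestone or has already had an event. Under 7.4 a patient still in response whose last scan was 8 months after first response has a censored DOR of 8 months. That is not longer than 9 or 12 months, so with all responders in the denominator the patient is scored with those who progressed. The reported figure then mixes how long responses last with how long patients have been watched.

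At stake is the descriptive statement on how long responses last. An early cut could make lasting responses look short, and a later cut of the same trial would give a higher figure with no change in the treatment effect.

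**Working it through.** The plan states no DOR figure, so there is none to reproduce. The check compares the raw percentage with Kaplan-Meier on the same data.

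**Inputs from the documents**
- 28 patients per arm (15 + 13) and response rates of 15% and 35% (section 7.1): 28 × 0.15 = 4.2 and 28 × 0.35 = 9.8 expected responders per arm.
- Scans every 12 weeks (section 6.1.1), so the first response is put at 2.8 months.
- Milestones of 6, 9 and 12 months and the censoring rule (section 7.4).

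**Assumptions not in the documents**
- Exponential DOR with median 12, 18 or 24 months.
- Uniform accrual over 18 or 24 months, and a cut at month 24, 30, 36 or 60 from study opening.
- No loss to follow-up, and censoring at the cut itself rather than at the last scan before it.

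**Small example.** Ten responders have times 3+, 4, 5+, 7+, 8, 10+, 11+, 14, 16+ and 20+ months (+ means censored in response).
- Raw: 7/10, 5/10 and 3/10, that is 70%, 50% and 30% beyond 6, 9 and 12 months.
- Kaplan-Meier: the event at 4 months has 9 at risk, giving 8/9 = 0.889. The event at 8 months has 6 at risk, giving 0.889 × 5/6 = 0.741. The estimates are 89%, 74% and 74%.
- Of the seven patients not counted at 12 months, five were censored without an event.

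**Formula.** With all responders in the denominator, the raw percentage estimates S(t) × P(F > t), where S is the true DOR survival function and F is follow-up after response. With accrual over A months and a cut at month T, P(F > 12) = (T − 14.8)/A, capped at 1. For median 18 months, S(12) = 0.5^(12/18) = 0.630:
- A = 18, T = 24: 9.2/18 = 0.511; 0.630 × 0.511 = 0.322.
- A = 24, T = 24: 9.2/24 = 0.383; 0.630 × 0.383 = 0.241.
- A = 24, T = 36: 21.2/24 = 0.883; 0.630 × 0.883 = 0.556.
- A = 24, T = 60: factor 1; 0.630.

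In the first case the raw 12-month figure would be only about 51% even if no response ever ended.

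**Simulation** (10 responders, 2,000 repetitions). Entries are the 12-month percentages true / raw / Kaplan-Meier.

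| Accrual, cut (months) | Median 12 | Median 18 | Median 24 | Raw shortfall (points) |
|---|---|---|---|---|
| 18, 24 | 50.0 / 25.5 / 49.4 | 63.0 / 32.6 / 62.5 | 70.7 / 36.4 / 71.1 | 24.5 to 34.3 |
| 24, 24 | 50.0 / 19.2 / 49.7 | 63.0 / 24.8 / 63.3 | 70.7 / 27.0 / 70.0 | 30.8 to 43.7 |
| 24, 30 | 50.0 / 31.4 / 50.3 | 63.0 / 39.9 / 63.0 | 70.7 / 44.7 / 70.4 | 18.6 to 26.0 |
| 24, 36 | 50.0 / 43.6 / 49.4 | 63.0 / 56.4 / 63.8 | 70.7 / 62.0 / 70.3 | 6.4 to 8.7 |
| 24, 60 | 50.0 / 49.7 / 49.7 | 63.0 / 63.0 / 63.0 | 70.7 / 71.1 / 71.1 | about 0 |

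The simulation agrees with the formula. With a cut at month 24, between 31% and 53% of responders are censored before 12 months. The earlier milestones are affected less: for accrual 18, cut 24 and median 18, the 6- and 9-month figures are 79.4% and 70.7% true, 67.1% and 47.9% raw, and 79.0% and 70.3% by Kaplan-Meier.

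One caution on the second row. It keeps responders enrolled in the last 2.8 months, whose first scan would fall after the cut. Without them P(F > 12) = 9.2/21.2 = 0.434, and the shortfall is 0.500 × 0.566 = 28 to 0.707 × 0.566 = 40 points. The upper end of 44 is therefore generous.

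**The case against.** The best defense is that the synopsis already commits to Kaplan-Meier for time-to-event variables, which DOR is, and also promises listings of individual data. This stands to the extent that one cannot say the plan nowhere calls for Kaplan-Meier on DOR. It does not remove the problem: the specific text in 7.4 makes the method discretionary, names no milestone estimates, and keeps the raw percentages alongside it. The two places conflict and need to be aligned.

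Second, 7.4 calls these patients censored and never says they count as short responders. That is correct. The understatement follows from the literal wording with all responders in the denominator; it is not a stated rule.

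Third, no cut-off is fixed for DOR. The 24-month sentence, "Study accrual will be sufficient to assess the primary endpoint within 24 months from the time the study opens to accrual", concerns accrual and the primary endpoint, and imaging can run to 36 months from the start of treatment. A late analysis would remove almost all administrative censoring before 12 months. This stands, and it is why the size is given as a range. Early censoring through new anti-cancer treatment or withdrawal could remain.

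Fourth, Kaplan-Meier from about 4 to 10 responders is imprecise. True, but a raw percentage rests on the same few patients, and a confidence interval shows the imprecision openly.

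A reader might also infer more than the documents support:
- That DOR is the trial's stated durability measure. Section 2.2 reads "Determine the durability of clinical benefits in patients treated with tavo-EP, pembrolizumab, and epacadostat" but continues "as assessed by time to progression, median PFS, median OS"; DOR is not named there or among the secondary endpoints in 2.4.2.
- That the clinical benefit rate has the same defect. Section 7.4 treats it as a proportion, like BORR, and counting patients without documented 6-month disease control as not meeting it is an ordinary conservative convention.
- That the arms would be biased differently. Both arms open together in Stage 1, no accrual schedule by arm is given, and 7.3 excludes formal testing between arms.

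**Conclusion.** The concern holds in a limited form. The DOR summary committed to in 7.4 is a raw milestone percentage of a censored variable, with no rule for early censoring. Taken literally, it understates durability whenever responders are censored before the milestone. The optional Kaplan-Meier sentence does not repair this and conflicts with the synopsis.

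The 12-month shortfall is about 24 to 44 points with a cut at month 24 (accrual 18 to 24 months). With accrual over 24 months it is 6 to 9 points with a cut at month 36 and about 0 at month 60. These figures rest on exponential DOR with median 12 to 24 months, uniform accrual, response at the first scan, no loss to follow-up, and all responders in the denominator. A reader might take a halving of the 12-month figure as the expected result; it belongs to the early-cut scenarios only, and the documents fix no such cut.

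The defect is confined to the DOR summary. The primary endpoint, the sample size, and the PFS and OS analyses are not affected.

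**What to change.** In section 7.4, replace the raw milestone percentages with Kaplan-Meier estimates and 95% confidence intervals of DOR at 6, 9 and 12 months. Show the number at risk and the number censored before each milestone. This brings 7.4 into line with the Statistical consideration row of the synopsis.

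If a crude percentage is kept, restrict its denominator to responders whose first response was at least 6, 9 or 12 months before the data cut, as the milestone requires. State how responders in that group who were censored early for other reasons are counted. Naming the DOR data cut-off would let readers judge how much administrative censoring remains.

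The cost is SAP wording only: no new data, visits or patients. The downside is imprecision with about 4 to 10 responders per arm. Kaplan-Meier also assumes that censoring is unrelated to prognosis, which may be doubtful for patients whose imaging stops at a new treatment; reporting the number censored before each milestone helps to show how much rests on this.

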7.5 Exploratory Analysis

The plan for the exploratory / translational endpoint is described in **Appendix 4**. Correlative analyses between exploratory/translational endpoint and clinical endpoints may also be conducted if warranted.

7.6 Safety Analysis

Safety analyses will be conducted on All Treated Subjects, by treatment arm and dose levels as appropriate, and overall. Safety analyses will be based on adverse events, clinical laboratory tests, physical examination, and vital sign measurements. All adverse event will be graded using CTCAE version 4 or later. Safety analyses will be summarized using descriptive statistics. Continuous measurements will be summarized using n (number of subjects with the measured quantity), mean, and standard deviation, median, minimum and maximum. Categorical measurement will be summarized by frequencies and percentages.

8 Restricted Medications

Restricted Medications/Treatment

- Systemic steroids may be used at doses \leq 10 mg/day prednisone or equivalents.
- Use of coumarin-based anticoagulants (eg, Coumadin) is discouraged. Low-dose Coumadin® (1 mg) is acceptable; however, doses that increase the INR are discouraged and will require routine monitoring.

Stable Baseline INR	Epacadostat Dose
	$\leq 300\text{mg BID}$
INR ≤ 2.5	Close INR monitoring
INR > 2.5	Close INR monitoring

- Use of the anticonvulsant carbamazepine (a UGT1A9 inducer) is discouraged. Because there is a potential interaction that could result in lower epacadostat exposures, an alternative to carbamazepine should be used, if possible.

Prohibited Medications/Treatment

Subjects are prohibited from receiving the following therapies starting from screening through end of treatment phase of this study unless otherwise noted below:

- Any investigational medication other than pembrolizumab, epacadostat, and tavo-EP.
- Use of any anticancer medications, including chemotherapy or biologic therapy other than the study medications.

- Any chronic immunological-suppressive treatment for any reason. (**Note:** Inhaled or topical steroids are allowed, and systemic steroids at doses ≤ 10 mg/day prednisone or equivalents are allowed and immune suppressants are allowed for short-term treatment for immune toxicities or as prophylaxis for contrast allergy for imaging procedures.)
- Radiation therapy

Note: In the presence of a mixed response (some lesions improving or stable and other lesions progressing), radiation therapy to a symptomatic solitary lesion or to the brain is allowed.

- Administration of a live attenuated vaccine within 30 days before the first dose of study treatment and while participating in the study. Examples of live vaccines include, but are not limited to, the following: measles, mumps, rubella, chicken pox, yellow fever, rabies, BCG, and typhoid vaccine. Seasonal influenza vaccines for injection are generally killed virus vaccines and are allowed; however, intranasal influenza vaccines (eg, FluMist®) are live attenuated vaccines and are not allowed.
- Use of any MAOI or drug associated with significant MAOI activity agents is prohibited from 21 days prior to Day 1 through 2 weeks after the final dose of epacadostat has been administered
- Use of any immunological-based treatment for any reason from screening through follow-up visit is prohibited.

Note: Completed adjuvant therapy (eg, vaccines) with principal investigator approval, inhaled or topical steroids, and systemic steroids at doses ≤ 10 mg/day prednisone equivalents are allowed, as described in Restricted Medications.

- Any UGT1A9 inhibitor, including acitretin, amitriptyline, androsterone, cyclosporine, dasatinib, diclofenac, diflunisal, efavirenz, erlotinib, estradiol (17-beta), flutamide, gefitinib, gemfibrozil, glycyrrhetic acid glycyrrhizin, imatinib, imipramine, ketoconazole, linoleic acid supplements, mefenamic acid, mycophenolic acid, niflumic acid, nilotinib, phenobarbital, phenylbutazone, phenytoin, probenecid propofol, quinidine, ritonavir, sorafenib, sulfapyrazone, valproic acid, and verapamil. Note: Propofol is allowed for short term sedation for biopsies.

Subjects may receive other medications that the investigator deems to be medically necessary.

The exclusion criteria describe other medications that are prohibited during this study. There are no prohibited therapies during the post-treatment follow-up phase.

9 Discontinuation of Therapy

The Investigator will withdraw a patient whenever continued participation is no longer in the patient's best interests. Reasons for withdrawing a patient include, but are not limited to, disease progression, the occurrence of an adverse event or a concurrent illness, a patient's

request to end participation, a patient's non-compliance or simply significant uncertainty on the part of the Investigator that continued participation is prudent. There may also be administrative reasons to terminate participation, such as concern about a patient's compliance with the prescribed treatment regimen.

